2.2 Secondary objectives

Secondary Objective:	Outcome Measure :
To develop prediction models and examine their ability to predict response to the study intervention based on baseline patient characteristics, such as sociodemographic, clinical, and medication use characteristics, as well as initial receptiveness to changing health behaviors	
Outcome Measure :
 
Predictive statistics:
 
 - Cross-validated C-statistics (discriminative ability of the model) - Cross-validated R-squares (explained variation in treatment response)

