For each outcome (e.g., $HbA1c < 8\%$ and $PDC \geq 0.80$), we will first estimate a model that includes only demographic and clinical characteristics. We will then estimate additional models that include these predictors as well as baseline medication adherence. Receipt of the pharmacist intervention will be tested using an interaction term so the logistic regression will provide estimates on all patients and not just those receiving the intervention. We will also repeat the analyses among the subgroup of intervention patients who had at least 1 telephonic encounter with a pharmacist to examine which set of characteristics are most predictive of the response to the intervention. Model estimation will be repeated among relevant patient subgroups (e.g., gender, age) to see if there are any differences in predictive ability.

Models among each of the control and intervention groups will be predicted using both logistic regression and generalized boosting regression, a data mining technique that generates a prediction model through building many regression trees with the potential for many interactions among the predictors.¹⁸ Through these many regression trees, the model can incorporate a number of non-linear associations between the predictors and the outcomes; this approach is considered to be one of the best prediction approaches. Alternative methods of clustering patients who are most likely to respond will also be explored, including machine learning to develop models algorithmically, to partition patients into clusters that have a similar likelihood of experiencing the clinical outcomes.¹⁹

Model accuracy:

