To compare the accuracy of the prediction models, we will compare discrimination, the ability of the model to distinguish between patients who do and do not experience the outcome, by the C-statistic. A C-statistic of 1.0 indicates perfect prediction and a value of 0.5 indicates no association.^{8,20} Pseudo R-squares will be used to assess model performance by examining the degree of variation explained by the model, ranging from 0 (no variation explained) to 1.0 (all variation explained)²¹. As secondary analyses, we will also model the change in HbA1c as well as continuous PDC at the end of the follow-up period using linear regression and boosted linear regression, using R-squares to examine predictive ability. To avoid "over optimism" bias associated with evaluating prediction accuracy in the same data used for estimation, we will perform 10-fold cross-validation, which randomly partitions a sample of data into different partitions (leaving 10% of the data out each time) 10 times and averages the validation results over the 10 repetitions.⁸

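### Aim 2 compares C-statistics and R-squares averaged over ten held-out tenths with no interval, so small differences cannot be told from noise and R-squares from sets of very different size are not comparable

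*SAP*

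**What the plan says.** Protocol 2.2 makes prediction of response the secondary objective. Its outcome measures are cross-validated C-statistics and "Cross-validated R-squares (explained variation in treatment response").

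SAP 4.2.2 (Model accuracy) compares models on discrimination, measured "by the C-statistic", and on a pseudo R-square for the binary outcomes. It adds linear models for HbA1c change and continuous PDC, "using R-squares to examine predictive ability". Validation is 10-fold, "leaving 10% of the data out each time", and the procedure runs "10 times and averages the validation results over the 10 repetitions". Protocol 8.1 has the same scheme.

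The models are fitted in several sets: all patients, each arm, the "subgroup of intervention patients who had at least 1 telephonic encounter with a pharmacist", and demographic subgroups. On the last, the SAP says: "Model estimation will be repeated among relevant patient subgroups (e.g., gender, age) to see if there are any differences in predictive ability".

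Neither document gives a standard error, interval or test for a C-statistic, an R-square or a difference between two of them. SAP 4.2.1, by contrast, attaches 95% confidence intervals to the Aim 1 effect estimates. SAP 1.3 calls the sample adequate for Aim 2 without a precision target.

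**The concern.** Two things could mislead a reader of the Aim 2 results.

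First, the plan invites comparative statements (this model predicts better, this subgroup is more predictable) with nothing to show how far sampling error alone would move the figures.

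Second, averaging over tenths is harmless for some measures but not for every R-square. If each tenth is scored against its own mean, the reference fits that tenth better than any mean known in advance could, and R-square is pushed down. The push grows as the tenth shrinks. A small set would then look less predictable than a large one for arithmetical reasons.

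Protocol 8.1 expects the results to tell payers and providers which patients may respond, so a spurious contrast could influence whom a programme targets.

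**Working it through.** **1. Size of the contacted-only set.** Inputs: 700 per arm and 25% loss (both documents), 45% reach (Protocol 8.2), 30% participation (SAP 1.3).

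- Protocol: 700 × 0.45 = 315, and 315 × 0.75 = 236.25. The Protocol states 315 and 236, so its figure reproduces.
- SAP rates: 700 × 0.30 = 210, and 210 × 0.75 = 157.5, or about 158.
- The 25% loss applies to observed HbA1c. It does not apply to PDC (SAP 3.3 expects no missing data) or to imputed HbA1c (SAP 3.1 and 3.2).

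The set is therefore 158, 210, 236 or 315 patients: about 16, 21, 24 or 32 per tenth. All patients with observed HbA1c number 1,400 × 0.75 = 1,050, or 105 per tenth. One arm, or an even split of the 1,050, is 525.

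**2. The own-mean effect in its simplest form.** Take a model with no predictors, which predicts the training mean. In a tenth of m patients, with 9m in training, the squared error exceeds the tenth's own SST by m(1/m + 1/(9m))σ² = (10/9)σ² on average. For normal outcomes the mean of σ²/SST is 1/(m − 3). The expected drop in 1 − SSE/SST is therefore (10/9)/(m − 3):

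| m | Formula | Simulated |
|---|---|---|
| 16 | 1.111/13 = 8.5 points | 8.5 |
| 21 | 1.111/18 = 6.2 | 6.2 |
| 24 | 1.111/21 = 5.3 | 5.3 |
| 32 | 1.111/29 = 3.8 | 3.8 |
| 105 | 1.111/102 = 1.1 | 1.1 |

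**3. The same effect with predictors.** Simulated linear models, 10-fold. True R-square differs between rows, so compare within a row only.

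| n | Predictors | Averaged over tenths | Pooled | Gap (points) |
|---|---|---|---|---|
| 158 | 5 | 0.109 | 0.198 | 8.9 |
| 210 | 5 | 0.002 | 0.064 | 6.2 |
| 210 | 14 | −0.048 | 0.019 | 6.7 |
| 315 | 14 | 0.003 | 0.043 | 4.0 |
| 1,050 | 5 | 0.220 | 0.230 | 1.0 |

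A further set with true R-square 15% and 5 or 14 predictors gave gaps of about 7–10 points at 158, 4–6 at 210–236, 3–4 at 315 and 1 at 1,050. A Brier-type pseudo R-square for binary outcomes showed much the same gaps.

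**4. The definition matters.** In the n = 158, 5-predictor run, averaging a squared correlation gave 0.253, against 0.198 pooled and 0.109 with own-mean averaging. The same data thus yield 11%, 20% or 25%, depending on a choice that the SAP leaves open.

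**5. Precision of C.** Hanley–McNeil: SE² = [A(1 − A) + (n₁ − 1)(Q₁ − A²) + (n₂ − 1)(Q₂ − A²)]/(n₁n₂), with Q₁ = A/(2 − A) and Q₂ = 2A²/(1 + A). At A = 0.65 with half the patients having the outcome, SE is 0.044 at 158, 0.024 at 525 and 0.017 at 1,050. Other settings at 158 gave 0.042–0.050 by formula, hence a 95% interval of about ±0.08 to ±0.10. Simulation gave 0.053 with 5 predictors and up to 0.068 with 20.

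For two independent groups of 525 with equal true C, the SE of the difference is √2 × 0.024 = 0.034. Then 0.05/0.034 = 1.47, and a gap above 0.05 in either direction has probability 0.14. With SE 0.025 it is 0.16. Hence about 15%.

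**6. Ranking models on the same patients.** At n = 158 the truly better model ranked first in 56–63% of runs for a true R-square gain of 0.02, 78–88% for 0.05 and 93–99% for 0.10. Averaged and pooled R-square ranked about equally well: at n = 210 with 14 predictors, 69.5% against 73.3% for a gain of 0.02, and 95.8% against 97.0% for 0.05.

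**The case against.** The strongest reply is that the bias rests on a reading. The SAP says only that validation results are averaged; it does not say that R-square uses each tenth's own mean. With the training-set mean as reference, still averaged by tenth, a check at n = 158 gave 18.1% against 20.0% pooled, so most of the gap disappears. This stands: the fault is an undefined measure that one natural choice would bias.

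Next, the contacted-only analysis asks which characteristics predict best within that set. The models share the same patients and tenths, so the bias largely cancels, and the SAP does not expressly plan to compare contacted-only R-squares with all-patient ones. This also stands. For the planned sex and age comparisons the artefact is small: in an assumed 420/630 split, R-squares were 20.0% and 21.3% (5 predictors), a gap of 1.3 points against 0.3 pooled, so about 1 point is due to averaging. The size effect matters when the contacted-only figure is read beside a much larger set.

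Aim 2 is also descriptive, with no decision threshold. That argues against a pass/fail rule, but not against intervals.

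A reader might infer that rankings in the contacted-only set are mostly chance. Step 6 does not support this: they are close to a coin toss only for gains of about 0.02. A reader might also infer that the SAP truncates R-square at zero, because it speaks of "examining the degree of variation explained by the model, ranging from 0 (no variation explained) to 1.0 (all variation explained"). That sentence explains a scale and sets no truncation rule.

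**Conclusion.** The point holds in a limited form. No interval is planned for any Aim 2 measure or difference, so small gains between models and modest subgroup gaps cannot be told from noise. R-square is undefined. Under own-mean averaging it is about 3 to 10 points below the pooled value in the contacted-only set, against about 1 point at 1,050 patients, so R-squares from those sets should not be set side by side. Model ranking within one set is largely unaffected.

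Sixteen per tenth should not be read as the size of the set. It is the low end of 16 to 32, and applies only to observed HbA1c at the SAP's 30% and 25%.

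The sizes rest on assumptions outside the documents: 5 to 14 predictors, true R-square around 10–15% in most runs, and normal predictors. Boosted models were not simulated. The missing intervals do not depend on any of this. The issue concerns the secondary objective only and leaves the primary analysis untouched, so it is a worthwhile improvement rather than a serious flaw.

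**What to change.** In SAP 4.2.2:

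- Compute each R-square once from all held-out predictions combined: 1 − SSE/SST for continuous outcomes, and the Brier-based equivalent, 1 − Σ(y − p)²/Σ(y − ȳ)², for binary ones. State that negative values are possible and will be reported.
- Report bootstrap 95% intervals for every C-statistic, R-square and difference: paired between models on the same patients, independent between subgroups. Keep all copies of a resampled patient in the same fold, so that no patient is in both training and held-out data.
- Describe differences in predictive ability in light of those intervals, without a significance rule.
- Repeating the 10-fold split is optional. It reduces partition noise only and does not replace an interval.

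The cost is SAP wording and computing time. No new data are needed. Some apparent differences will be reported as inconclusive.

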5. INTERIM ANALYSES

N/A

6. CHANGES OF ANALYSIS FROM PROTOCOL

N/A

8. APPENDIX

N/A
